14.3 Study Implementation

This study will be conducted in accordance with the protocol, international good clinical practice guidelines, and all applicable US and local regulations. Study implementation will also be guided by the IMPAACT MOP, study-specific MOP, LPC, and other study implementation materials, which will be available on the study-specific website:

https://impaactnetwork.org/studies/IMPAACT2032.asp

Study implementation at each site will also be guided by site-specific SOPs. The DAIDS policy on Requirements for Manual of Operations specifies the minimum set of SOPs that must be established at sites conducting DAIDS funded and/or sponsored clinical trials (available on the website referenced in Section 11.2). These SOPs should be updated and/or supplemented as needed to describe roles, responsibilities, and procedures for this study.

14.4 Protocol Deviation Reporting

Per the policy for Requirements for Source Documentation in DAIDS Funded and/or Sponsored Clinical Trials (available at the website referenced in Section 11.2), all protocol deviations must be documented in participant research records. Reasons for the deviations and corrective and preventive actions taken in response to the deviations should also be documented.

Deviations should be reported to the sIRB and any other applicable review bodies in accordance with the policies and procedures of these review bodies; this includes the sIRB, per the prompt reporting requirements available at the website cited in Section 7.1.1. Serious deviations that are associated with increased risk to one or more study participants and/or significant impacts on the integrity of study data must also be reported within IMPAACT, following procedures specified in the IMPAACT MOP.

14.5 Critical Event Reporting

Per the DAIDS policy on Identification and Classification of Critical Events, a critical event is defined as an unanticipated study-related incident that is likely to cause harm or increase the risk of harm to participants or others or has a significant adverse impact on study outcomes or integrity. All such events must be reported following procedures specified in the DAIDS Critical Events Manual, which is available at:

https://www.niaid.nih.gov/sites/default/files/criticaleventsmanual.pdf

14.6 ClinicalTrials.gov

This protocol is subject to the United States Food and Drug Administration Amendments Act of 2007 (FDAAA), including registration in ClinicalTrials.gov.

15 PUBLICATIONS

All presentations and publications of data collected in this study are governed by IMPAACT policies, which are available in the IMPAACT MOP.

Appendix I Schedule of Evaluations

	Baseline				Infu	sion	Safety Follow-up⁴			Delivery 4,5		
Period	Screening / Entry ¹	Pre- infusion ²	First	Second	Third	Fourth	Fifth	Post- Fifth ³	48-hours Post Last Infusion	7-Days Post Last Infusion	4-Weeks Post Last Infusion	(Arm 1 ONLY)
CLINICAL DATA COLLECTION												
Informed Consent/Subject Enrollment System	X											
Medical and Medications History/Chart Abstractions ⁶		X	X	X	X	X	X	X	X	X	X	X
LABORATORY DATA COLLECTION ⁶												
Chemistries - Cr, eGFR, ALT, AST, alk phos, bilirubin		X	X	X	X	X	X	X	X	X	X	
Albumin			X	X	X	X	X	X				
Coagulation factors – (PT, INR, PTT)		X	X	X	X	X	X	X	X	X	X	
Hematology – CBC with differential and platelets		X	X	X	X	X	X	X	X	X	X	
Other laboratory test results		X	X	X	X	X	X	X	X	X	X	X
Inflammatory markers - (LDH, procalcitonin, ESR, CRP, hs CRP, D-dimer, ferritin, troponin I, hs troponin I)		[X]	[X]	[X]	[X]	[X]	[X]	[X]				
PHARMACOLOGY												
Intensive PK plasma sampling ⁷					[16 mL]	[16 mL]	[16 mL]					
Intracellular PK sampling (store DBS, PBMC) ⁷					[18 mL]	[18 mL]	[18 mL]					
Protein binding plasma sample ^{7,8}					[6 mL]	[6 mL]	[6 mL]					

	Baseline		Infusion						Safety Follow-up⁴			Delivery 4,5
Period	Screening / Entry ¹	Pre- infusion ²	First	Second	Third	Fourth	Fifth	Post- Fifth ³	48-hours Post Last Infusion	7-Days Post Last Infusion	4-Weeks Post Last Infusion	(Arm 1 ONLY)
CLINICAL DATA COLLECTION												
Alpha-1 acid glycoprotein ⁹					[X]	[X]	[X]					
Single PK sampling with SOC labs (plasma)				2 mL ¹⁰	[2 mL] ¹⁰	[2 mL] ¹⁰	[2 mL] ¹⁰		[2 mL] ¹¹			
Breast milk sample ¹²					[5 mL] ¹³	[5 mL] ¹³	[5 mL] ¹³		[5 mL] ¹¹			
Single maternal delivery PK sample (plasma) ¹⁴												[2 mL]
Cord blood PK sample ¹⁴												[2 mL]
TOTAL MAXIMUM PK BLOOD VOLUME	0 mL	0 mL	0 mL	2 mL	40 mL	40 mL	40 mL	0 mL	2 mL	0 mL	0 mL	4 mL

^[] indicate procedures that are not required at each time indicated or not for all participants.

APPENDIX I FOOTNOTES

- 1. Entry may occur at any point after hospitalization and prior to the start of the 4th infusion.
- 2. Pre-infusion period is defined as 48 hours prior to start of first infusion. Collect data retrospectively if enrollment occurs after this 48-hour window has started or passed.
- 3. For any participants whose treatment is continued past the 5th infusion, clinical and laboratory data will be abstracted and recorded for each infusion day while infusions are ongoing per Section 6.4.
- 4. The Safety Follow-up Period may occur before or after Delivery. For Arm 1 women, if Delivery occurs within the Safety Follow-up Period, data for both periods should still be collected and reported.
- 5. Delivery procedures are for Arm 1 women only. If an RDV infusion was NOT given within 5 days preceding delivery, PK sampling will not be performed. Delivery period is from onset of labor through 24-hours after delivery.
- 6. See Section 6 for data collection requirements for each period.
- 7. Only perform intensive PK sampling schedule once, with the 3rd, 4th or 5th infusion. See Section 6.4.1 for collection timepoints.
- 8. Collect only once on the intensive PK day, with the pre-dose sample only.
- 9. To be measured from leftover blood sample used for DBS, see LPC.
- 10. Collect when blood samples are drawn as part of clinical care (preferably prior to infusion administration on that day) if no SOC bloods are drawn on a given day, single PK sample may be collected if circumstances permit, but if unable to collect, the sample may be omitted for that day. Do not collect on the day that intensive PK sampling is performed.

- 11. Only collect samples for women still hospitalized. If the participant has already been discharged, omit this sample collection. If still hospitalized and if possible, collect single PK sample when blood samples are drawn as part of clinical care. If no bloods are drawn on this day for clinical care, draw blood specifically for single PK sample. See Section 6.5.
- 12. Only for women who have consented to provide breast milk samples, and only if women are lactating at the time of PK sampling.
- 13. Collect only one breast milk sample, on the intensive PK day. See Section 6.4.1 for collection timepoints. 5 mL is the optimal volume, but any volume >0.5 mL will be accepted.
- 14. Only perform if RDV received within 5 days prior to delivery. See Section 6.6.1 for collection details.

1.1 Purpose

This Primary Statistical Analysis Plan (SAP) describes the primary and secondary outcome measures of the IMPAACT 2032 study that will be included in the primary manuscript. These outcome measures address the major primary and secondary objectives of the study. The Primary SAP outlines the general statistical approaches that will be used in the analysis of the study. It has been developed to facilitate discussion of the statistical analysis components among the study team and to provide agreement between the study team and statisticians regarding the statistical analyses to be performed and presented in the Primary Analysis Report. It also describes the results for the primary and secondary outcome measures that will be posted on ClinicalTrials.gov.

Detailed outlines of tables, figures, and coding descriptions that will be included in the Primary Analysis Report are included in the Analysis Implementation Plan (AIP). The pharmacokinetic (PK) analyses to be performed by the IMPAACT 2032 protocol pharmacologist(s) are described in the Pharmacology Statistical Analysis Plan (PK SAP).

Analyses for the Primary Analysis Report will be finalized once the last participant has completed data collection for all primary outcome measures, i.e., the last study visit (primary completion date, PCD) and all queries have been resolved.

Outlines of analyses for other objectives and outcome measures not included in the Primary SAP will be provided in a separate SAP.

1.2 Version History

Current document is Version 2.0, based on Protocol Version 2.0, dated 18 December 2020.

Major modifications from Version 1.0 include the addition of Section 5 "Estimands and Estimation".

2 Study Overview

2.1 Study Design

IMPAACT 2032 is a Phase IV prospective, open label, non-randomized opportunistic study to describe the pharmacokinetic (PK) properties and safety of remdesivir (RDV) administered intravenously as part of clinical care among hospitalized pregnant and non-pregnant women with coronavirus disease of 2019 (COVID-19). RDV will be provided and managed by the participant's treating physician and will not be provided as part of this study. This study is comprised of 2 arms specific to the study population. Arm 1 includes pregnant women, while Arm 2 includes non-pregnant women of childbearing potential. PK sampling will be performed during the RDV infusions and women will be followed for safety for 4 weeks after the last infusion; Arm 1 women who are still pregnant at that time will have an additional follow-up at the time of delivery.

The target sample size is 20 PK-evaluable women for each arm (defined in **Section 4** below). If a participant is deemed unevaluable for PK, the Clinical Management Committee (CMC) will determine how to proceed with replacement. There is no randomization or stratification in this study.

The primary and secondary objectives are to describe the pharmacokinetics of RDV and its metabolite, GS-441524, in plasma after administration to pregnant and non-pregnant women as part of clinical care and to describe clinical and laboratory safety outcomes through 4 weeks postlast infusion in pregnant and non-pregnant women receiving RDV as part of clinical care and during delivery in pregnant women. Other objectives that will be addressed in separate SAP(s) are listed in Section 2.2 of the protocol (Version 2.0).

A challenge in designing this study is the current paucity of data on the PK parameters of RDV and its metabolites (e.g., GS-441524, GS-704277, and GS-443902) and their variability, particularly when given to adults with COVID-19, and how they might differ during pregnancy. While pregnancy is expected to alter RDV and GS-411524 drug disposition, the differences in RDV PK in pregnant versus non-pregnant women are not expected to be of sufficient magnitude to require dosing modifications from the standard adult doses of RDV. A preliminary analysis approach for this study is to assess if drug exposure during pregnancy is within 30% of the PK outcome measure(s) for a comparison population of non-pregnant adults, including healthy non-COVID-19 infected adults, adults with COVID-19, and non-pregnant women enrolled in Arm 2 of this study. Additional analyses to assess adequacy of dosing during pregnancy will be performed as more information on the PK and pharmacodynamics of RDV in adults with COVID-19 becomes available, including data from Arm 2 (non-pregnant women) of this study. These analyses will be addressed in a separate SAP.

This study design is opportunistic because it enrolls women who may have received at least one infusion of RDV. Consequently, the results may be overly optimistic. Because participants can be enrolled any time before the 4th infusion, the study population might not include women who started RDV and discontinued it before the 4th infusion due to toxicity, intolerance, virologic failure, or any other reason. Thus, this study may not identify pharmacokinetic, safety, or tolerance issues that occur soon after drug initiation and estimates of the frequency of adverse outcomes may be overly optimistic. The fact that the results of this study may not generalize to the full population of women who start RDV will be discussed as a limitation of the study in presentations and publications of results.

2.2 Hypotheses

As the study objectives are descriptive, the study protocol does not specify any hypotheses.

2.3 Study Objectives

This Primary SAP addresses the following primary and secondary objectives listed in the study protocol. Other study objectives in the protocol will be addressed in separate SAP(s).

2.3.1 Primary Objectives

- 1. Arm 1: Describe the pharmacokinetics of RDV and its metabolite, GS-441524, after administration to pregnant women as part of clinical care.
- 2. Arm 1: Describe the clinical and laboratory safety outcomes through 4 weeks postinfusion and during delivery in pregnant women receiving RDV as part of clinical care.

2.3.2 Secondary Objectives

- 1. Arm 2: Describe the pharmacokinetics of RDV and its metabolite, GS-441524, after administration to non-pregnant women of childbearing potential as part of clinical care.
- 2. Arm 2: Describe clinical and laboratory safety outcomes through 4 weeks post-infusion in non-pregnant women of childbearing potential receiving RDV as part of clinical care.

2.4 Overview of Sample Size Considerations

The target number of participants in each arm is 20 PK-evaluable women. This target was selected based on sample size calculations regarding the ability of the study to indicate whether the PK outcome measures in pregnant women are within 30% of the PK outcome measures for non-pregnant comparison populations. We also calculated the precision provided for estimating the risk of adverse events.

To determine an appropriate sample size for the PK primary objective, we considered the precision for estimating the PK parameter with different target sample sizes, as measured by the width of the resulting confidence intervals (CI) expressed as a percentage of the mean value. CIs were calculated using the modified Cox approach (Olsson, 2017). At the time of protocol development, there were limited PK data available for RDV in humans (EMA, 2020, Humeniuk 2020, Tempestelli 2020). Coefficient of variation (CV) estimates for RDV and GS-441524 AUCs and C_{max} presented in the European Medicines Agency's summary on compassionate use range from 12.7% to 30.3% (i.e., 0.127 to 0.303), based on data from healthy adult non-pregnant volunteers. Because the Protocol Team expects study participants will have a wider range in age, disease severity, and stage of pregnancy (for Arm 1), resulting in a higher variability than the available data, we describe the precision with an assumed CV of 0.2, 0.3, or 0.4.

Table 1 below illustrates the upper and lower confidence limits and width of the 90% CI for the mean PK parameter (e.g., area under the plasma concentration curve, half-life, or trough concentration), expressed as a percentage of the mean, for different N and CV. With a sample size of 20 evaluable women and a CV equal to 0.3, the 90% CI will range from 89 – 112.3% of the mean, and the corresponding CI width will be 23.3% of the mean. This relatively narrow CI would provide a very good indication of whether our data suggest a greater than 30% difference from the PK parameter in non-pregnant comparison populations.

N	CV = 0.2		CV = 0.3		CV = 0.4	
Ν	Range	Width	Range	Width	Range	Width
15	91.3- 109.5%	18.2%	87.2-114.6%	27.4%	83.4- 120.0%	36.6%
20	92.6- 108.0%	15.5%	89.0- 112.3%	23.3%	85.7-116.7%	31.1%
25	93.4- 107.1%	13.7%	90.2- 110.8%	20.6%	87.2-114.7%	27.5%

Table 1. Percentile range and width of 90% CIs for the mean PK parameter

For the safety primary objective, we calculated the precision for potential proportions of participants experiencing Grade 3 or higher adverse events or adverse pregnancy outcome that may be observed and the probability of observing events with sample sizes ranging from 15 to 25. Table 2 below presents the exact binomial (Clopper-Pearson) 95% upper and lower confidence limits. With a sample size of 20 evaluable women and an observed adverse event rate of 20%, the 95% CI will range from 6% - 44%.

Table 2. Precision (exact binomial 95% Cls) for estimating the percentage of participants experiencing a ≥ Grade 3 adverse event or adverse pregnancy outcome

Ν	n (%) with ≥Grade 3 Adverse Events or Adverse Pregnancy Outcome	Exact 95% CI
15	0 (0%)	0% - 22%
20	0 (0%)	0% - 17%
25	0 (0%)	0% - 14%
15	2 (13%)	2% - 40%
20	2 (10%)	1% - 32%
25	3 (12%)	3% - 31%
15	3 (20%)	4% - 48%
20	4 (20%)	6% - 44%
25	5 (20%)	7% - 41%
15	5 (33%)	12% - 62%
20	6 (30%)	12% - 54%
25	8 (32%)	15% - 54%
15	6 (40%)	16% - 68%
20	8 (40%)	19% - 64%
25	10 (40%)	21% - 61%
15	8 (53%)	27% - 79%
20	10 (50%)	27% - 73%
25	13 (52%)	31% - 72%

Additional sample size details are provided in Section 9.4.1 of the protocol (Version 2.0).

2.5 Formal Interim Monitoring

No formal interim analyses were planned or specified in the study protocol. The plans for study monitoring are described in Section 9.5 of the protocol (Version 2.0).

3 Outcome Measures

3.1 **Primary Outcome Measures (Arm 1)**

- 1. [For Primary Objective 1] Non-compartmental PK parameters:
 - a. RDV area under the plasma concentration-time curve (AUC)
 - b. RDV half-life (t_{1/2})
 - c. GS-441524 trough concentration (Ctrough)
- 2. [For Primary Objective 2] Clinical and laboratory safety outcomes:
 - a. Maternal renal adverse events of any grade through 7 days post-last infusion
 - b. Maternal hepatic adverse events of any grade through 7 days post-last infusion
 - c. Maternal hematologic events of any grade through 7 days post-last infusion
 - d. Adverse events through 4 weeks post-last infusion and during delivery:
 - i. Maternal Grade 3 or higher adverse events
 - ii. Serious adverse events
 - iii. Maternal Grade 3 or higher adverse events assessed as related to RDV by the CMC
 - e. Labor/delivery outcomes:
 - i. Pregnancy loss
 - ii. Congenital anomalies
 - iii. Preterm birth (< 37 weeks, < 34 weeks)
 - iv. Small for gestational age (SGA) (< 10th percentile for gestational age)
 - f. Newborn physical exam:
 - i. Birth weight
 - ii. Length
 - iii. Head circumference

Note: Additional non-compartmental PK parameters, described in Table 2 of the PK SAP, will also be summarized for Arm 1 as part of the Primary Analysis Report for RDV, GS-441524, and/or GS-704277 (data permitting).

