1.3 Rationale

Although pregnant women are routinely excluded from COVID-19 experimental treatment protocols, the care providers of pregnant women who develop severe COVID-19 are treating them with potential therapies in the absence of pregnancy specific PK and safety data and outside of research protocols. Under these circumstances, the fastest way to get the urgently needed RDV pregnancy PK and safety data is through an opportunistic RDV PK and safety protocol in pregnant women receiving RDV as part of clinical care. IMPAACT 2032 will follow the opportunistic design of the highly successful IMPAACT P1026s study which between 2004 and 2019 performed intensive PK sampling and safety evaluations for HIV and TB therapeutics in over 1000 pregnant and postpartum women, successfully evaluating the PK and safety of over 25 different HIV and TB medications in pregnant and postpartum women. Because of the duration of treatment of HIV and TB, participants in IMPAACT P1026s were studied both during pregnancy and postpartum, serving as their own controls. This approach is not possible with RDV, which has a treatment duration of 5-10 days. As a result, women treated during pregnancy will generally not be receiving the drug postpartum. Under these circumstances the best comparison group for PK and safety data from pregnant women would be data from non-pregnant adult women of childbearing potential. Since such data are lacking for RDV, IMPAACT 2032 will also simultaneously enroll and study RDV PK and safety in a cohort of COVID-19 positive, non-pregnant women of childbearing potential. These nonpregnant participants will provide the first data describing RDV PK and safety in women receiving RDV for COVID-19 and will serve as a comparison group for the IMPAACT 2032 pregnant women.

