7.2.2 Adverse Events

The following adverse events that meet the criteria and specific to the time periods listed below will be entered into Adverse Event log eCRFs.

Infusion and Safety Follow-up Periods:

- Infusion reactions of any grade
- All Grade 3 and higher events
- All SAEs as defined in Version 2.0 of the DAIDS EAE Manual

Arm 1: Delivery Period (onset of labor through 24 hours after delivery):

- All congenital anomalies of the infant
- All Grade 3 and higher events

• All SAEs as defined in Version 2.0 of the DAIDS EAE Manual

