Arm 2		 RDV AUC RDV T1/2 GS-441524 C_{trough} Renal adverse events of any grade through 7 days post-last infusion Hepatic adverse events of any grade through 7 days post-last infusion Hematologic events of any grade through 7 days post-last 	
Arm 2		 RDV AUC RDV T1/2 GS-441524 C_{trough} Renal adverse events of any grade through 7 days post-last infusion Hepatic adverse events of any grade through 7 days post-last infusion Hematologic events of any grade through 7 days post-last infusion 	
Arm 2		 RDV AUC RDV T1/2 GS-441524 C_{trough} Renal adverse events of any grade through 7 days post-last infusion Hepatic adverse events of any grade through 7 days post-last infusion Hematologic events of any grade through 7 days post-last infusion Adverse events through four weeks post-last infusion and during delivery: Grade 3 or higher adverse events 	
Arm 2		 RDV AUC RDV T1/2 GS-441524 C_{trough} Renal adverse events of any grade through 7 days post-last infusion Hepatic adverse events of any grade through 7 days post-last infusion Hematologic events of any grade through 7 days post-last infusion Adverse events through four weeks post-last infusion and during delivery: Grade 3 or higher adverse events Serious adverse events 	
Arm 2		 RDV AUC RDV T1/2 GS-441524 C_{trough} Renal adverse events of any grade through 7 days post-last infusion Hepatic adverse events of any grade through 7 days post-last infusion Hematologic events of any grade through 7 days post-last infusion Adverse events through four weeks post-last infusion and during delivery: Grade 3 or higher adverse events 	
	9.2.2.2	 RDV AUC RDV T1/2 GS-441524 C_{trough} Renal adverse events of any grade through 7 days post-last infusion Hepatic adverse events of any grade through 7 days post-last infusion Hematologic events of any grade through 7 days post-last infusion Adverse events through four weeks post-last infusion and during delivery: Grade 3 or higher adverse events Serious adverse events 	
Arm 2 Other Outcom	9.2.2.2	 RDV AUC RDV T1/2 GS-441524 C_{trough} Renal adverse events of any grade through 7 days post-last infusion Hepatic adverse events of any grade through 7 days post-last infusion Hematologic events of any grade through 7 days post-last infusion Adverse events through four weeks post-last infusion and during delivery: Grade 3 or higher adverse events Serious adverse events Grade 3 or higher adverse events assessed as related to 	

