3.2 Secondary Outcome Measures (Arm 2)

- 1. [For Secondary Objective 1] Non-compartmental PK parameters:
 - a. RDV AUC
 - b. RDV t_{1/2}
 - c. GS-441524 Ctrough

- 2. [For Secondary Objective 2] Clinical and laboratory safety outcomes:
 - a. Renal adverse events of any grade through 7 days post-last infusion
 - b. Hepatic adverse events of any grade through 7 days post-last infusion
 - c. Hematologic events of any grade through 7 days post-last infusion
 - d. Adverse events through 4 weeks post-last infusion:
 - i. Grade 3 or higher adverse events
 - ii. Serious adverse events
 - iii. Grade 3 or higher adverse events assessed as related to RDV by the CMC

Note: Additional non-compartmental PK parameters, described in Table 2 of the PK SAP, will also be summarized for Arm 2 as part of the Primary Analysis Report for RDV, GS-441524, and/or GS-704277 (data permitting).

4 General Considerations

The derivation of PK parameters will be performed by the IMPAACT 2032 protocol pharmacologist(s), as described in the PK SAP. The statistical summaries to be prepared by the statisticians are described in this Primary SAP.

For primary and secondary PK analyses, the PK Evaluable analysis set will be used. This analysis set will include women who have at least 3 out of 4 of the pre-dose through 3 hours postend-of-infusion (post-EOI) intensive PK samples, either the 5 hours post-EOI or the 7 hours post-EOI intensive PK sample, and either the pre-dose or 23 hour post-EOI samples collected. In addition to these minimum requirements for sample collections, drug concentrations will also be reviewed once available to further assess whether the participant is PK evaluable. PK evaluability will be determined by the protocol pharmacologists and CMC on a case-by-case basis. If a participant is deemed unevaluable for PK, the CMC will determine how to proceed with replacement. For primary and secondary safety analyses, the Safety analysis set will be used. This analysis set includes all women who receive any amount of RDV.

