5.1 Primary Estimands

5.1.1 First Primary Estimand

Primary Objective 1: To describe the pharmacokinetics of RDV and its metabolite, GS- 441524, after administration to pregnant women as part of clinical care		
Estimand description Geometric mean of PK parameter (RDV AUC/RDV t _{1/2} / GS-441524 C _{trough}) ir hospitalized pregnant woman, who tolerated at least 3 RDV infusions for the treatment of COVID-19.		
Treatment Remdesivir (RDV)		
Target population	Analysis set	
Hospitalized pregnant women who received and	PK-evaluable women	
tolerated at least 3 RDV infusions for treatment	(PK Evaluable analysis set)	
of COVID-19	NOTE: Women will be considered PK evaluable if they have at least 3 out of 4 of the pre-dose through 3 hours post-end-of- infusion (post-EOI) intensive PK samples, either the 5 hours post-EOI or the 7 hours post-EOI intensive PK sample, and either the pre-dose or 23 hour post-EOI samples collected. In addition to these minimum requirements for sample collections, drug concentrations will also be reviewed once available to further assess whether the participant is PK evaluable. For t _{1/2} , women will be PK evaluable if they have the additional requirement of 3 consecutive declining points in the curve.	
Variable(s)	Outcome measure(s)	
1. RDV concentration in plasma	Non-compartmental PK parameters:	
2. RDV concentration in plasma	1. RDV area under the plasma	
3. GS-441524 concentration in plasma	concentration-time curve (AUC) 2. RDV half-life (t _{1/2})	
	3. GS-441524 trough concentration	
	(Ctrough)	
Handling of intercurrent events	Handling of missing data	
The following intercurrent events are relevant to	Only participants who are deemed PK	
the estimand:	evaluable will be included in the final	
1. Onset of labor	analysis (i.e., missing observations due to	
2. Discontinue treatment for toxicity or non-toxicity reasons	missing or inadequate sampling are considered missing completely at random).	
3. Maternal death		

These intercurrent events will be addressed using a principal stratum approach.	Participants who do not undergo intensive PK sampling will not be included in the final analysis (i.e., missing observations due to drop out prior to intensive PK sampling are considered missing completely at random).
	Given the descriptive nature of the primary analyses, there are no planned supplementary or sensitivity analyses.
Population-level summary measure	Analysis approach

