5.2.2 Second Secondary Estimand

Secondary Objective 2: To describe the clinical and laboratory safety outcomes through 4 weeks post-infusion in non-pregnant women of childbearing potential receiving RDV as part of clinical care.		
Estimand description	(A) Probability of a non-pregnant woman of childbearing potential, who received any amount of RDV while hospitalized for the treatment of COVID-19,* having at least one adverse event (renal/hepatic/hematologic of any grade) or death through 7 days post last infusion.	
	(B) Probability of a non-pregnant women of childbearing potential, who received any amount of RDV while hospitalized for the treatment of	

Treatment	 COVID-19,* having at least one adverse event (Grade 3 or higher/serious/Grade 3 or higher assessed as related by the CMC) or death through 4 weeks post last infusion and at delivery. *NOTE: This study design is opportunistic in that it enrolls women who may have already received at least one infusion of RDV. Because participants can be enrolled any time prior to the 4th infusion, the study population will potentially not include women who started RDV and discontinued it prior to the 4th infusion due to toxicity, intolerance, virologic failure, or any other reason. Consequently, the results may be overly optimistic. Remdesivir (RDV) 		
Target population		Analysis set	
Non-pregnant women of childbearing potential who received any amount of RDV while hospitalized for treatment of COVID-19* *NOTE: This study design is opportunistic in that it enrolls women who may have already received at least one infusion of RDV. Because participants can be enrolled any time prior to the 4 th infusion, the study population will potentially not include women who started RDV and discontinued it prior to the 4 th infusion due to toxicity, intolerance, virologic failure, or any other reason. Consequently, the results may be overly optimistic.		Non-pregnant women who received any amount of RDV (Safety analysis set)	
Variable(s)		Outcome measure(s)	
 (A) Occurrence of each of the following through 7 days post-last infusion: 1. Renal adverse events of any grade 2. Hepatic adverse events of any grade 3. Hematologic adverse events of any grade 		Outcome measures as defined by the variables	
through 4 weeks 1. Grade 3 2. Serious a 3. Grade 3 assessed CMC	f each of the following post-last infusion: or higher adverse events adverse events or higher adverse events d as related to RDV by the		

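### Arm 1 adverse-event outcome 2d merges a 4-week window and a delivery window into one proportion, with inconsistent definitions, a denominator that biases the rate upward, and a serious-event item open to infant events

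*SAP*

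**What the plan says.** **Arm 1.** SAP 3.1, outcome 2d, is headed "Adverse events through 4 weeks post-last infusion and during delivery". Items (i) and (iii) are restricted to maternal events. Item (ii), serious adverse events, is not.

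**Arm 2.** SAP 3.2, outcome 2d, reads "Adverse events through 4 weeks post-last infusion" and has no delivery component. Two other places disagree. Protocol Table 7 (Section 9.2) uses "Adverse events through four weeks post-last infusion and during delivery" for the non-pregnant arm too, and the estimand description in SAP 5.2.2(B) runs "or death through 4 weeks post last infusion and at delivery".

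**Estimand.** In SAP 5.1.2(B) the description, the variable and the summary measure all include delivery. The analysis approach stops at 4 weeks.

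**Missing data.** SAP 5.1.2 treats as missing, and removes from the denominator, any woman who leaves follow-up before the time point of interest without an event. For part (B) that time point is 4 weeks and delivery together.

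**Infant events.** Protocol 7.2.2 sends "All congenital anomalies of the infant" to the adverse event log during the Delivery period. Protocol 4.5 gives infants no identifier and records their data on the mother's forms.

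**7-day outcomes.** SAP 3.1, item 2c, is "Maternal hematologic events of any grade through 7 days post-last infusion"; 2a and 2b are the renal and hepatic counterparts. None says how a delivery inside the window is handled. SAP 5.1.1 lists "Onset of labor" as an intercurrent event for PK. SAP 5.1.2 lists only maternal death and a terminal fetal or infant event.

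**Role of Arm 2.** Protocol 1.3 states that "the best comparison group for PK and safety data from pregnant women would be data from non-pregnant adult women of childbearing potential".

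**The concern.** Women may enroll at any gestational age, so the Delivery period can follow the last infusion by days or by months. Protocol 6.5 says that data in the gap are generally not collected. The 2d proportion therefore covers two separate stretches of time whose spacing depends on gestational age at enrollment.

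Three things are at stake. First, the primary rate is not uniquely defined, because the estimand and its analysis approach use different windows. Second, tying the denominator to delivery discards complete 4-week data from event-free women only. Third, a reader who sets the two arms side by side, as the rationale invites, compares 4 weeks plus delivery with 4 weeks. In the serious-event row an infant event may also count as the woman's.

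**Working it through.** **1. The plan's own precision figure.** SAP Table 2 gives 6% to 44% for 4 of 20. The Clopper-Pearson limits are 5.7% and 43.7%, so it reproduces. All 18 rows of that table match after rounding.

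**2. Windows side by side.**

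| Place | Arm 1 | Arm 2 |
|---|---|---|
| Protocol Table 7 | 4 weeks + delivery | 4 weeks + delivery |
| SAP 3.1 / 3.2, outcome 2d | 4 weeks + delivery | 4 weeks |
| SAP 5.1.2(B) / 5.2.2(B), description | 4 weeks + delivery | 4 weeks + delivery |
| Same, summary measure | 4 weeks + delivery | 4 weeks |
| Same, analysis approach | 4 weeks | 4 weeks |

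The Arm 1 analysis approach departs from every other Arm 1 entry. Two Arm 2 entries carry a delivery window that non-pregnant women cannot have.

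**3. Denominator.** The documents give no loss rate, so these counts are assumed. Take 20 women with complete 4-week data, 4 with an event by then and 16 without. Four of the 16 are lost before delivery.

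- No delivery events: the rule gives 4/(20 − 4) = 4/16 = 25%, against 4/20 = 20% with everyone counted.
- Delivery-period event risk of 10% among event-free women: full follow-up gives (4 + 16 × 0.10)/20 = 5.6/20 = 28%. The rule gives (4 + 12 × 0.10)/16 = 5.2/16 = 32.5%.

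The shift is upward because only event-free women can be removed.

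**4. Effect of adding the delivery window.** Let p be the 4-week rate and q the additional rate from a later delivery (and, in the serious-event row, from the infant). Assume independence: P = 1 − (1 − p)(1 − q). The documents give no q, so a range is shown for p = 20%.

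| q | P | P/p | Share of counted women with only a delivery or infant event, (P − p)/P | Nearest count of 20 (exact 95% CI) |
|---|---|---|---|---|
| 5% | 24% | 1.2 | 17% | 5 (9–49%) |
| 10% | 28% | 1.4 | 29% | 6 (12–54%) |
| 20% | 36% | 1.8 | 44% | 7 (15–59%) |
| 30% | 44% | 2.2 | 55% | 9 (23–68%) |

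Over the same q, P runs from 14.5% to 37% at p = 10% and from 33.5% to 51% at p = 30%. Arm 1 could exceed Arm 2 with identical 4-week risk.

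**5. One infant event.** If one infant anomaly is classed as serious and counted in the woman's row, 0/20 (upper limit 17%) becomes 1/20 (upper limit 25%).

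**The case against.** The strongest reply is that delivery is there by design. Objective 2.1.2 in the protocol covers 4 weeks and delivery, so a proportion over both answers the stated question. That stands, and it is why the pooled row should stay. It also makes the absence of labor from the intercurrent events in SAP 5.1.2 defensible: labor interrupts a PK profile, but it lies inside the period this safety variable describes.

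A reader might infer that Arm 1 safety as a whole is contaminated, or that the rates fail to describe remdesivir safety. The documents do not support that. Items 2a–c, 2d(i) and 2d(iii) are maternal only. Labor/delivery outcomes and newborn measurements are separate outcomes with their own estimands. Item 2d(iii) isolates the Grade 3 or higher events that the Clinical Management Committee judges related.

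A reader might also infer that the plan will attribute a between-arm safety difference to pregnancy. It will not: the comparative objectives concern PK and intracellular concentrations, and SAP 2.2 specifies no hypotheses. What remains is informal side-by-side reading.

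Other mitigation is partial:

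- Presentation by trimester (SAP Section 4) partly separates women near term.
- The best-case imputation in SAP 5.1.2 would bring the 4/16 example back to 4/20 = 20%. The worst case gives 8/20 = 40%, a wide bracket for a 4-week question with complete data.
- The Analysis Implementation Plan, not among the documents, may already contain extra rows or event coding.
- Protocol 7.2 applies the adverse event definition to participants, and infants are not enrolled. Whether infant events enter the serious-event row is therefore unsettled, not established. An anomaly appearing in two separate proportions is not double counting within either.

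None of this resolves the mismatch within SAP 5.1.2(B) or the denominator rule.

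**Conclusion.** The point holds for outcome 2d and estimand 5.1.2(B), with minor to moderate severity. The Arm 1 window is defined in two ways, the Arm 2 window is misdescribed in two places, and it is not stated whose serious events count. The missing-data rule biases the pooled rate upward whenever event-free women are lost between 4 weeks and delivery. The sizes are illustrations: 20% becoming 25% assumes four such losses among 20 women, and 24% to 44% assumes a 20% 4-week rate with an independent added delivery or infant rate of 5% to 30%. At 20 women per arm the intervals overlap heavily, so the gain is a clear definition rather than detection of a difference.

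The 7-day outcomes are a lesser matter. The protocol allows delivery during infusions or follow-up and records blood counts of any grade, so blood loss at delivery could register as a hematologic event. The documents do not show how often.

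**What to change.** 1. **Split the window.** In SAP 5.1.2(B), report each 2d item through 4 weeks, with denominator women who have 4-week follow-up or an event by then, and separately for the Delivery period. Keep the pooled row. In the assumed example the 4-week row returns 4/20. State that an event at a delivery within the 4 weeks appears in both rows, since the 4-week row matches Arm 2 in length but is not free of delivery events.
2. **Reconcile the texts.** Align protocol Table 7, SAP 3.1 and 3.2, and all parts of 5.1.2(B) and 5.2.2(B). Remove delivery from the Arm 2 wording.
3. **Separate mother and infant.** Report maternal and infant serious events in separate rows. Simply restricting the item to the mother would lose information, because the labor/delivery list covers only pregnancy loss, anomalies, preterm birth and small size for gestational age. Any other serious infant event would have no row.
4. **Optional.** For the 7-day any-grade outcomes, add a row counting only events before labor begins or a Cesarean starts.

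Cost: SAP wording and a few extra rows with small counts. Event and delivery dates are already collected.
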